5.2. Feasibility Study

We will collect data related to the number of participants approached and consented; the percentage consented who attend the facilitated workshop, the number of activities the participants at the workshop have completed, the number of participants who take part in the exit interview and the progress made towards goals set at the Sensemaking Workshop. We will also explore the intervention's potential to improve patient-reported outcomes including patient global impression of change (PGIC). Patient-reported outcomes will be measured before and after the intervention.

5.2.1. Hypothesis

≥80% of participants attending the facilitated workshop will have completed at least 2 of the 3 reflective tools.

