1.1. Synopsis

Title:	Toward Thriving Study
Grant Number:	N/A
Study Description:	A longitudinal clinical trial in a cohort of chronic pain to assess feasibility of a new behavioral intervention based on the principles of positive psychology. The study will recruit 20 participants, who will complete 4 timepoints (T1-T4). Participants will be consented at T1. T2 will be a kickoff meeting for all participants. After T2, participants will complete study intervention phase 1 (cultural probe kit) for three weeks. Next participants will participate in a facilitated workshop at T3, complete phase 2 of the intervention, followed by an exit interview at T4. Participants will complete a study survey at T1 and T4.
Objectives*:	The purpose of this pilot study is to introduce and test a positive psychology intervention meant to empower chronic pain patients and help support their resiliency and thriving.
Endpoints*:	
 Primary: Feasibility and acceptability of the behavioral intervention (cultural probe kit related activities). Percent (%) of participants engaging in the intervention between T1 and T4 Secondary: Change in PGIC between T1 and T4 Change in PROMIS Pain Interference between T1 and T4 Exploratory: Change in PROMIS 29 depression, anxiety sleep, fatigue between T1 and T4
Study Population:	Participants over the age of 18 with chronic pain
Description of Sites/Facilities Enrolling Participants:	This study will recruit patients at the Michigan Medicine. There will be no sites outside of the US.
Description of Study Intervention/Experimental Manipulation:	Participants will complete a cultural probe kit over 3-weeks. This kit is a design research tool, to prompt participants to document, map, journal, and reflect on various aspects of their daily lives
Study Duration*:	12 months
Participant Duration:	4 months

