3.4.3. Incentives

Participants will be paid up to \$250. They will receive \$150 for completing the workshop (T3) and associated intervention phase 1 kit and \$100 for completing the exit interview and associated phase 2 activities

4. Study Intervention

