4.2. Phase 1 and Workshop (T3)

Participants will be using a cultural probe kit, a design research tool, to prompt participants to document, map, journal, and reflect on various aspects of their daily lives. During an interactive, in-person workshop (T3), participants will review and synthesize the contents of their probe kit and set goals for themselves. The workshop, which takes place after participants have completed three weeks of at-home activities, will be facilitated in small groups by a designer and psychologist team.

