5.2.2. Outcome

The primary outcome is the proportion of participants who attending the Sensemaking Workshop have completed at least 2 of the 3 reflective tools. The secondary outcomes are patient's belief about the efficacy of intervention (PGIC) and other symptoms including pain interference, depression, anxiety, and sleep, etc. The rate of patients being lost-to-follow-up will also be tracked to aid in appropriate design of a future randomized clinical trial.

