6.1. Discontinuation of Study Intervention

Discontinuation from the intervention will be considered withdrawal from the study as well. This is further described below.

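### The synopsis and section 5.2 define the primary feasibility outcome differently, and missing the T3 workshop cannot count against the ≥80% hypothesis

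*Combined protocol and SAP*

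**What the plan says.** The synopsis (1.1) names feasibility and acceptability as primary and gives the measure as "Percent (%) of participants engaging in the intervention between T1 and T4". It sets no threshold, does not define engaging, and does not restrict the count to workshop attendees.

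Section 5.2.1 states the feasibility hypothesis: "≥80% of participants attending the facilitated workshop will have completed at least 2 of the 3 reflective tools". Section 5.2.2 repeats the restriction: "The primary outcome is the proportion of participants who attending the Sensemaking Workshop have completed at least 2 of the 3 reflective tools".

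Section 5.2 also plans to collect the percentage of consented participants who attend the workshop, "the number of activities the participants at the workshop have completed", and "the number of participants who take part in the exit interview". Section 5.2.2 adds tracking of loss to follow-up, and section 5.2.3 plans frequencies for feasibility data. None of these has a target, and none enters the 80% hypothesis. Activity counts are listed only for people at the workshop.

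The workshop (T3) follows the first three weeks of home activities (4.2). Three more weeks of activities come after it, before T4 (4.3). Section 5.1.2 separately names an acceptability outcome as primary.

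**The concern.** Whether people who are given the kit use it is a central feasibility question for a pilot that is meant to help design a randomised trial. As written, the only quantified feasibility hypothesis can be met while kit use among all recipients is well below 80%, or is unknown for those who did not come. A reader also cannot tell whether the synopsis or section 5.2 answers the primary feasibility question.

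A second issue is conditional. If people who did not use the kit tend to stay away from T3, the attendee proportion overstates kit use. Three features of the plan make that plausible:

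- At the workshop "participants will review and synthesize the contents of their probe kit and set goals for themselves", which gives someone with an empty kit less reason to come.
- A single payment is made "for completing the workshop (T3) and associated intervention phase 1 kit" (3.4.3).
- Significant non-compliance is a ground for withdrawal (6.2), and "Discontinuation from the intervention will be considered withdrawal from the study as well" (6.1), so some non-users may be gone before T3.

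**Working it through.** **1. The two definitions side by side**

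| | Synopsis (1.1) | Sections 5.2.1 and 5.2.2 |
|---|---|---|
| Denominator | participants | T3 workshop attendees |
| Window | T1 to T4 | up to T3 |
| Measure | engaging, undefined | at least 2 of 3 tools completed |
| Threshold | none | ≥80% |

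The documents do not list the three tools. That they belong to Phase 1 is inferred from timing: completion assessed at T3 cannot include activities that come later.

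**2. Inputs**

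- From the documents: 20 participants (1.1) and the 80% threshold (5.2.1).
- Assumed: all 20 receive the kit, and a point estimate of at least 80% is read as meeting the hypothesis, since the plan gives no formal success rule.
- Not given: any expected attendance or completion rate. Attendance is therefore varied. There is no figure in the plan to reproduce.

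**3. Smallest result that meets the threshold, re-expressed over all 20**

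With a attendees, the smallest qualifying count is m = 0.8a rounded up. Confirmed completion among all 20 is m/20. If every absentee had in fact completed, it would be (m + 20 − a)/20.

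| Attend (a) | m | m/a | m/20 | (m + 20 − a)/20 |
|---|---|---|---|---|
| 20 | 16 | 80% | 80% | 80% |
| 19 | 16 | 84% | 80% | 85% |
| 18 | 15 | 83% | 75% | 85% |
| 16 | 13 | 81% | 65% | 85% |
| 15 | 12 | 80% | 60% | 85% |
| 12 | 10 | 83% | 50% | 90% |

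Exact (Clopper-Pearson) 95% CIs: 13/16, 54.4-96.0%, against 13/20, 40.8-84.6%; and 10/12, 51.6-97.9%, against 10/20, 27.2-72.8%.

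**4. When the attendee proportion is biased**

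Let q be true completion, c the attendance probability of completers and p that of non-completers. The probability that an attendee is a completer is qc / (qc + (1 − q)p). If p = c this equals q, so there is no bias.

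With q = 0.6 and c = 0.9 it is 0.54 / (0.54 + 0.4p):

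| p | Expected attendee proportion | P(attendee estimate ≥80%) |
|---|---|---|
| 0.9 | 60% | 0.04 |
| 0.6 | 69% | 0.20 |
| 0.3 | 82% | 0.62 |

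The last column is an exact trinomial sum with n = 20. If completion were known for all 20, P(at least 16/20) would be 0.051.

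**5. The opposite case**

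Take q = 0.9, with 80% attending for unrelated reasons (c = p = 0.8). The attendee rule is met with probability 0.91. With completion known for all 20, P(at least 16/20) is 0.96. If every absentee is counted as not completed, the success probability is 0.9 × 0.8 = 0.72 and P(at least 16/20) is 0.30.

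**The case against.** The strongest reply is that the established defect is a mismatch of definitions, and that much of the missing denominator can be recovered. Section 5.2 already collects the attendance percentage and the attendees' activity counts. Their product gives confirmed completion over all participants; with 16 of 20 attending, (16/20) × (13/16) = 13/20. Heavy absence would be reported, not hidden. This stands. But the quantity is not named as the outcome, it does not enter the hypothesis, and no section plans to collect kit use from people who miss the workshop.

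A reader might go further and infer that the attendee proportion does overstate kit use. The documents do not support that. They give no attendance rates and do not say that non-users stay away. T3 is in person, so people may miss it for unrelated reasons, and the payment and the rescheduling of missed visits (6.3) both support attendance. The 0.62 figure needs only 30% of non-completers to attend, with about 13 of 20 present overall (20 × (0.54 + 0.12) = 13.2).

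The error also runs both ways. In the opposite case above, the attendee rule (0.91) is closer to the full-data value (0.96) than a rule counting every absentee as not completed (0.30). And at this size even 16/20 has an exact 95% CI of 56-94%, so the threshold discriminates poorly under either denominator. These points weigh against a bare rule of counting absentees as failures. They do not remove the need to state one denominator.

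**Conclusion.** The concern holds in two parts of different strength.

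- **Established from the text:** the synopsis and section 5.2 define the primary feasibility outcome differently in denominator, window and measure, and absence from T3 cannot count against the 80% hypothesis. The size depends on attendance: nothing at 20 of 20, little at 18 or 19, and 81% against a confirmed 65% when 16 attend and 13 of them have completed. This assumes that all 20 receive the kit and that the point estimate decides.
- **Conditional:** upward bias in the attendee proportion requires non-users to attend less often than users. That is plausible from the plan's own arrangements but not established, and its size cannot be estimated from the documents.

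This should be fixed. The study can run as it stands, but its primary feasibility result is ambiguous.

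**What to change.** State the same feasibility outcome in the synopsis, 5.2.1 and 5.2.2:

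- **Outcome and denominator:** the number completing at least 2 of 3 tools by T3, divided by all eligible consented participants given the kit, with an exact 95% CI. Apply the 80% hypothesis to this proportion.
- **Outside the denominator:** list separately any consented participants found ineligible (3.3) or never given the kit, who may be replaced under 6.2.
- **Supportive results:** report the attendee-only proportion and the attendance rate among those consented, as 5.2 already plans to collect.
- **Absentees:** ask about tool completion at the missed-visit contact in 6.3 and when a withdrawal is recorded on the off-study form (6.2). The second route is needed because the missed-visit contact does not clearly reach people withdrawn before T3.
- **Remaining unknowns:** show both bounds, with unknowns counted as not completed and as completed.
- **Window:** do not drop Phase 2 from the synopsis endpoint by default. Either define T1-T4 engagement on the same denominator, or state explicitly that the primary window ends at T3.
- **Hierarchy:** state that acceptability (5.1.2) is a separate co-primary domain.

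The cost is protocol wording and one question added at existing contact points. Self-reported completion from an absentee is weaker evidence than a kit seen at the workshop. The reported rate may be less favourable, and counting unknowns as not completed understates kit use when absence is unrelated to it. That is why both bounds and the attendee proportion should be shown.

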5.2.2. Outcome

The primary outcome is the proportion of participants who attending the Sensemaking Workshop have completed at least 2 of the 3 reflective tools. The secondary outcomes are patient's belief about the efficacy of intervention (PGIC) and other symptoms including pain interference, depression, anxiety, and sleep, etc. The rate of patients being lost-to-follow-up will also be tracked to aid in appropriate design of a future randomized clinical trial.

5.2.3. Hypothesis test and power analysis

Frequencies will be calculated related to feasibility data (e.g., number of participants approached, consented, and take part in the workshop). Descriptive statistics of patient-reported outcomes will be calculated before and after the intervention. Paired t-tests are used on patients' changes from T1 to T4. Wilcoxon test will be applied if departure from the assumption of normality. Hypotheses tests are two-sided performed at the 5% significance level. 95% confidence interval will be conducted. Power analysis for efficacy is based on t-tests.

6. Study Intervention Discontinuation and Participant Discontinuation/Withdrawal

6.1. Discontinuation of Study Intervention

Discontinuation from the intervention will be considered withdrawal from the study as well. This is further described below.

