5.1. Acceptability Study

We will conduct semi-structured interviews to understand participant perception of the intervention at T4. We will assess the proportion of participants who report that the intervention was relatively easy to understand after orientation, low burden (easy to do), and potentially effective.

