5.1.1. Hypothesis

≥80% of participants will report that the intervention was relatively easy to understand after orientation, low burden, and potentially effective.

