5.1.2. Outcome

The primary outcome is the patient assessment of the cultural probe tool and the overall experience including orientation and facilitated workshop. A series of prompts in the semi-structured interview will elicit opinions about the intervention, the ease of completion, and the possibility that it could help promote positive emotions and resilience.

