6.2. Participant Discontinuation/Withdrawal from the Study

Participants are free to withdraw from participation in the study at any time upon request.

An investigator may discontinue or withdraw a participant from the study for the following reasons:

- Significant study intervention non-compliance
- If any clinical adverse event (AE), laboratory abnormality, or other medical condition or situation occurs such that continued participation in the study would not be in the best interest of the participant
- Disease progression which requires discontinuation of the study intervention
- If the participant meets an exclusion criterion (either newly developed or not previously recognized) that precludes further study participation

The reason for participant discontinuation or withdrawal from the study will be recorded on the off-study Case Report Form (CRF). Subjects who sign the informed consent form but do not receive the study intervention may be replaced. Subjects who sign the informed consent form, and receive the study intervention, and subsequently withdraw, or are withdrawn or discontinued from the study, will not be replaced.

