6.3. Lost to Follow-Up

A participant will be considered lost to follow-up if he or she fails to complete the study visits and scheduled surveys and are unable to be contacted by the study site staff after three attempts at any point in the study.

The following actions must be taken if a participant fails to return to the clinic for a required study visit:

- The site will attempt to contact the participant and reschedule the missed visit within a 2-week timeframe and counsel the participant on the importance of maintaining the assigned visit schedule and ascertain if the participant wishes to and/or should continue in the study.

- Before a participant is deemed lost to follow-up, the investigator or designee will make every effort to regain contact with the participant (where possible, 3 telephone calls, text message and, if necessary, a certified letter to the participant's last known mailing address or local equivalent methods). These contact attempts should be documented in the participant's study record.
- Should the participant continue to be unreachable, he or she will be considered to have withdrawn from the study with a primary reason of lost to follow-up.

7. Study Assessments and Procedures

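### Stopping the intervention ends study participation, so people who stop would be expected to give no T4 acceptability rating, and section 5.1 does not say whether they count in the 80% target

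*Combined protocol and SAP*

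**What the plan says.** Section 6.1 is unconditional: "Discontinuation from the intervention will be considered withdrawal from the study as well". Section 6.2 adds that the investigator may, but need not, withdraw someone for "Significant study intervention non-compliance". The reason for leaving is entered on an off-study form. People who received the intervention "and subsequently withdraw, or are withdrawn or discontinued from the study, will not be replaced".

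The acceptability data come from one source: "We will conduct semi-structured interviews to understand participant perception of the intervention at T4" (5.1). The hypothesis in 5.1.1 is that "≥80% of participants will report that the intervention was relatively easy to understand after orientation, low burden, and potentially effective". Section 5.1.2 makes this a primary outcome and extends it to "the overall experience including orientation and facilitated workshop". In the Schedule of Activities, PGIC appears only at T4, and PROMIS at T1 and T4.

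Section 6.3 asks the site to contact people who miss a visit and "reschedule the missed visit within a 2-week timeframe". Sections 5.2 and 5.2.2 count exit-interview participants and track loss to follow-up. Section 4.3 allows T4 to be virtual. The feasibility target in 5.2.1 names its denominator (workshop attendees); the acceptability target in 5.1.1 speaks only of participants.

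**The concern.** Finding the kit burdensome is a plausible reason to stop, and stopping takes a person out of the only described source of burden ratings. Whether a rating is missing may therefore depend on what the rating would have been. The recorded reason for leaving may show that burden played a part, but it does not replace a rating.

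What follows depends on the denominator. Among those interviewed, the proportion leans towards the intervention if non-acceptors stop more often than acceptors, leans against it if acceptors stop more often, and is unbiased but less precise if stopping is unrelated to acceptability. Over all participants, with an absent interview counted as not reporting, the figure is lower and there is no favourable lean. Since 5.1 leaves the choice open, the same data can meet or miss the target. PGIC and follow-up PROMIS would be missing for the same people.

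**Working it through.** **Inputs.** N = 20 (Synopsis); target 80% (5.1.1). The documents give no dropout rate, true acceptability or power figure for this outcome, so there is no stated result to reproduce. Stop rates and true acceptability below are assumptions shown over a range. All 20 are assumed to have received the kit.

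**Step 1: what the denominator does.** With m people interviewed, the fewest endorsers that reach 80% among them is k = ceil(0.8 × m). The bounds over all 20 are k/20 (missing counted as not endorsing) and (k + 20 − m)/20 (missing counted as endorsing).

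- 2 missing: 15/18 = 83.3%; bounds 15/20 = 75% and 17/20 = 85%.
- 4 missing: 13/16 = 81.3%; bounds 13/20 = 65% and 17/20 = 85%.
- 6 missing: 12/14 = 85.7%; bounds 12/20 = 60% and 18/20 = 90%.

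A result above the minimum can also straddle the target. With 4 missing and 14 of 16 endorsing, the figure is 87.5% (Clopper-Pearson 95% CI 61.7% to 98.4%), with bounds 14/20 = 70% and 18/20 = 90%. If missing counts as not endorsing, 5 or more missing makes the target unreachable, since 15/20 = 75%.

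**Step 2: effect of selective stopping on the interviewee proportion.** Let p be true acceptability, n the stop rate in non-acceptors and a the stop rate in acceptors. Each person is an interviewed acceptor with probability p(1 − a), an interviewed non-acceptor with probability (1 − p)(1 − n), or missing. The expected observed proportion is p(1 − a) / [p(1 − a) + (1 − p)(1 − n)]. The chance of observing at least 80% is the exact trinomial sum for N = 20.

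| Stop rate n / a | p = 65% | p = 80% | p = 90% |
|---|---|---|---|
| 0 / 0 | 11.8% | 63.0% | 95.7% |
| 25% / 10% | 18.0% | 65.2% | 94.5% |
| 25% / 0 | 21.2% | 71.7% | 97.0% |
| 50% / 10% | 44.0% | 84.9% | 98.3% |
| 50% / 0 | 50.0% | 87.9% | 99.0% |
| 25% / 25% | 12.6% | 55.4% | 90.3% |
| 0 / 25% | 3.75% | 36.5% | 82.3% |

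For the 25% / 10% row at p = 65%, the expected observed proportion is 0.585 / (0.585 + 0.2625) = 69.0%, with 20 × (1 − 0.8475) = 3.05 people missing on average. At p = 90% the expected proportion still rises, to 0.81 / (0.81 + 0.075) = 91.5%. The chance of reaching 80% nevertheless falls slightly, because there are fewer ratings.

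**Step 3: the same 25% / 10% case over all 20.** Missing counts as not endorsing, so the number endorsing is Binomial(20, p × 0.90) and 16 are needed. The chances are 3.8%, 30.2% and 67.3% at p = 65%, 80% and 90%, each below the no-dropout row. On this denominator there is no favourable lean.

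**The case against.** A reader might infer that the plan builds in an inflated acceptability figure. The documents do not support that. The Synopsis uses the word participants for the 20 recruited, and 5.2.1 shows that the plan names a subset when it means one. Read literally, someone who is never interviewed has not reported a favourable view and counts against the target. That reading is plausible, but 5.1 neither adopts it nor says how a missing interview counts.

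A reader might also infer that nothing will be known about those who leave. That goes too far: the reason is recorded, and interview numbers and loss to follow-up are tracked, so rough bounds could be rebuilt from the report. None of this supplies a rating.

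The affected group is limited. Section 6.3 may recover people who drift out of contact, and people who skip activities but stay enrolled can still reach T4. Sampling error at this size is also large: the illustrative bounds of 70% to 90% lie inside the 61.7% to 98.4% interval. These points stand and lower the severity. They do not remove the problem, because a confidence interval among those interviewed does not allow for selective absence.

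Finally, section 2.4 announces exit-interview plans, and Appendix A is only a heading in the available copy. Either could provide for contact after stopping. If so, it needs to be reconciled with 6.1.

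**Conclusion.** The concern holds in a limited form. As written, people who stop or are withdrawn would be expected to have no T4 acceptability rating, PGIC or follow-up PROMIS, and 5.1 does not settle how they enter the 80% target. A favourable lean is conditional on two things that the documents do not establish: that the denominator is those interviewed, and that non-acceptors stop more often than acceptors.

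The size is unknown. Under the mixed 25% / 10% assumption the change in the chance of observing 80% is about 6 percentage points at true acceptability 65%, 2 points at 80% and minus 1 point at 90%. Among the cases tried, it reaches 50% at true 65% only when half of non-acceptors and no acceptors stop. Severity is minor to moderate: this is a 20-person pilot, and no rule in the available text makes a later trial depend on the 80%. The change is worth making because it costs little.

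**What to change.** In 6.1 and 6.2, state that stopping or not complying with the activities does not by itself end data collection. Unless consent is withdrawn, or all participation has ended for another 6.2 reason, the person is still invited to the T4 survey and exit interview, virtually if preferred. When or why someone stops the activities is unchanged.

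In 5.1, name the denominator of the 80% target and say how a missing interview counts. Report:

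- the proportion among those interviewed, with its exact 95% CI;
- the number who received the kit but were not interviewed, with recorded reasons;
- bounds over all who received the kit, counting missing ratings first as not endorsing and then as endorsing.

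People who stopped before T3 cannot rate the workshop. They should rate only what they received and be shown separately, with the proportion given with and without them.

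The cost is some protocol wording and a few extra contacts among at most 20 people. The figure may come out lower, the bounds will be wide if several people are missing, and ratings from early stoppers will be partial. Section 3.4.3 ties $100 to the exit interview together with the phase 2 activities, so the payment wording, and any matching consent wording, would have to be aligned for people who did not complete phase 2.

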3.2. Exclusion Criteria

- Cancer
 - History of any bone-related cancer or cancer that metastasized to the bone
 - Currently in treatment for any cancer or plan to start cancer treatment in the next 12 months
 - History of any cancer treatment in the last 24 months
- Active substance abuse
- Uncontrolled depression or psychosis
- Visual or hearing difficulties that would preclude participation
- Individuals started receiving disability or compensation within the past year, or currently involved in litigation
- Current/planned (in the next 2 years) enrollment in another study of a device or investigational drug that would interfere with this study, this may include participation in a blinded trial.
- Any other diseases or conditions that would make a patient unsuitable for study participation as determined by the site principal investigators. This would include but not be limited to severe psychiatric disorders, active suicidal ideations or history of suicide attempts, and an uncontrolled drug and/or alcohol addiction)

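### Stopping the intervention ends study participation, and no PROMIS or PGIC is sought afterwards; the T1–T4 comparisons then rest on completers, with a bias of uncertain direction that is cheap to reduce

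*Combined protocol and SAP*

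**What the plan says.** Section 6.1 is a rule rather than a gap: "Discontinuation from the intervention will be considered withdrawal from the study as well". Section 6.2 opens its list with "An investigator may discontinue or withdraw a participant from the study for the following reasons" and names four:

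- poor adherence, worded as "Significant study intervention non-compliance";
- worsening illness, worded as "Disease progression which requires discontinuation of the study intervention";
- an exclusion that is newly met, or noticed only later, and rules out going on;
- a medical problem, from an adverse event to an abnormal laboratory result, where in the investigator's judgement "continued participation in the study would not be in the best interest of the participant".

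One exclusion in 3.2 is "Uncontrolled depression or psychosis". Section 6.2 also lets participants leave on request at any time. The reason is recorded on an off-study form, and those who had received the intervention are not replaced.

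On measurement, the synopsis says: "Participants will complete a study survey at T1 and T4". The schedule of activities (1.3) puts PROMIS at T1 and T4 and PGIC at T4 only. Section 5.2.3 plans paired t-tests on the T1–T4 changes, or a Wilcoxon test if normality fails. It names no analysis set and no method for missing scores. The contact attempts in 6.3 concern missed visits and unreachable participants, not people already withdrawn.

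**The concern.** A participant who stops the kit activities, or is stopped, leaves the study before the only follow-up survey. There is no interim score to fall back on, and a T4 score that was never requested cannot be recovered at analysis. A paired test uses only people with both scores, so these sections together produce a completers analysis, although the plan never calls it that.

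Some of the listed reasons are close to the outcomes. A participant whose depression becomes uncontrolled may be withdrawn before the follow-up depression score, and depression is an outcome (exploratory in the synopsis, secondary in 5.2.2). If such cases occur, the change in pain interference and mood describes those who did well enough to stay, and the PGIC answers lack the people most likely to report no benefit. Section 5.2.2 also says that loss to follow-up is tracked to help design a randomised trial. Whether people who stop will still answer a survey is useful for that design, and the present rule prevents the team from finding out.

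**Working it through.** **Inputs from the documents.** 20 participants (synopsis); PROMIS at T1 and T4 only (1.3); paired test, two-sided 5% (5.2.3), so 2.5% in the direction of improvement; no replacement after the intervention has been received (6.2). The plan gives no effect size, SD, power or dropout rate, so it has no figure of its own to reproduce.

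**Assumptions, none from the documents.** True mean change is zero. Change scores are normal with SD 1, and a negative change is improvement. Each participant has a withdrawal trigger = ρ × change + √(1 − ρ²) × noise, and the k participants with the highest triggers leave without a T4 score. Positive ρ means that worsening drives withdrawal; negative ρ means that improvement does.

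**Size of the bias.** The expected largest and second-largest of 20 standard normal values are 1.867 and 1.408. The completers' mean is therefore displaced by:

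- k = 1: ρ × 1.867/19 = 0.098ρ, or 0.03, 0.05 and 0.07 SD at ρ = 0.3, 0.5 and 0.7.
- k = 2: ρ × (1.867 + 1.408)/18 = 0.182ρ, or 0.05, 0.09 and 0.13 SD.

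**Effect on the test, by simulation (at least 100,000 trials per case; rates agree between runs to about 0.2 percentage points).**

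| Withdrawn | ρ | Bias in mean change | Chance of falsely significant improvement | 95% CI coverage |
|---|---|---|---|---|
| 1 or 2 | 0 | none | 2.5% | 95% |
| 1 | 0.3 to 0.7 | 0.03–0.07 SD towards improvement | 3.3–5.2% | not tabulated |
| 2 | 0.3 | 0.05 SD towards improvement | 4.2% | 94.3% |
| 2 | 0.5 | 0.09 SD towards improvement | 6.0% | 92.8% |
| 2 | 0.7 | 0.13 SD towards improvement | 8.7% | 90.4% |
| 2 | −0.3 | 0.05 SD against improvement | about 1.5% | as for 0.3 |
| 2 | −0.5 | 0.09 SD against improvement | a little over 1% | as for 0.5 |

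For scale, the standard error with 18 completers is 1/√18 = 0.236 SD. A bias of 0.05–0.13 SD is thus about 0.2–0.5 of a standard error. If the SD of change is 6–8 T-score points (assumed), two linked withdrawals shift the mean by 0.054 × 6 = 0.3 to 0.127 × 8 = 1.0 points.

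**Second method.** Bias = (w/20) × gap, where w is the number withdrawn and gap is the difference in mean change between completers and those withdrawn. With w = 2 and gaps of 0.25, 0.5 and 1.0 SD in favour of completers, the bias is 0.025, 0.05 and 0.10 SD, and the false-improvement rate is 3.2–6.0%. With w = 4 and a gap of 0.5 SD, bias is 0.10 SD and the rate 5.7%. Only an extreme case (w = 6, gap 1.0 SD) gives a bias above one standard error: 0.30 SD against 1/√14 = 0.27 SD, with a rate of 17.9%.

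**What retrieval buys (k = 2, ρ = 0.3–0.7).** If each withdrawn participant gives a T4 score with probability one half, the bias is 0.03–0.06 SD and the rate 3.4–5.1%. At three quarters, 0.01–0.03 SD and about 2.8–3.7%. With full retrieval the rate returns to about 2.5%.

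**The case against.** The strongest reply is that the direction is unknown. Section 6.2 also allows withdrawal on request for any reason and for non-compliance, neither of which is tied to worsening, and people who feel better may stop too. This stands, and it is why the negative-ρ rows belong in the table.

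Second, the triggers may seldom operate. The wording is permissive and partly generic: it mentions laboratory abnormalities, though 1.3 schedules no laboratory tests. The intervention is two three-week blocks of home activities plus a workshop, described as minimal risk (7.2, 7.5.3). Disease progression counts only if it requires stopping, and a new exclusion only if it precludes participation. This also stands; there may be few withdrawals or none.

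Third, the affected outcomes are secondary or exploratory, no decision rule depends on the paired tests, and a single-arm pilot could not attribute change to the intervention anyway. This sets the grade at minor.

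Fourth, part is already handled. Missed visits are pursued (6.3), reasons for withdrawal are recorded (6.2), and workshop attendance, exit interviews and loss to follow-up are counted (5.2, 5.2.2). What remains is the T4 score of people who are withdrawn but still reachable. That is probably a small group, but it is the one part that analysis cannot repair.

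A reader might go further and infer that the rule also inflates the two 80% criteria. The documents do not support making that part of this point. The workshop criterion is defined among attendees whatever 6.1 says (5.2.1, 5.2.2), and acceptability comes from the T4 interview (5.1). A request for PROMIS and PGIC would change neither proportion.

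**Conclusion.** The concern holds as a minor one. As written, 6.1 and 6.2 lead to T1–T4 comparisons in completers, with no later chance to obtain the missing scores. That is an inference: the plan does not forbid a T4 survey after withdrawal or name a completer set, but it provides for nothing else.

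A reader might infer that results will be biased in the intervention's favour. The documents support less than that. Several listed reasons point to worsening, but others do not, and no withdrawal rate is given. Under the assumed model, two linked withdrawals move the mean change by 0.05–0.13 SD towards improvement, with a false-improvement rate of 4.2–8.7% against 2.5%. The same number leaving because they feel better moves it by 0.05–0.09 SD the other way. Unrelated withdrawals, or none, give no bias. The case for acting rests on the low cost of asking and the fact that unsought scores are lost for good, not on a large expected error.

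**What to change.** In 6.1 and 6.2, separate stopping the intervention from leaving the study, and make the investigator's reasons in 6.2 grounds for stopping the intervention, so that the two sections agree. Add:

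*Participants who stop or are withdrawn from the intervention will still be asked to complete the T4 PROMIS survey and PGIC (virtually if preferred), unless they withdraw consent or the investigator documents that the survey itself would harm them.*

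The exemption is deliberately narrower than the best-interest reason in 6.2; otherwise it could excuse the very participants whose worsening would cause the bias.

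In 5.2.3, state that the paired tests use all available T4 scores from everyone who started the intervention. Beside each result, report the number without a T4 score, by reason taken from the off-study form.

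The cost is a few sentences and a few extra requests for an existing survey. T4 may already be done virtually (4.3), and no new visit or instrument is needed. Some requests will go unanswered and some participants will be exempted, so bias is reduced rather than removed.
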